9.2.2 Expected Adverse Events

- Corneal inflammation
- Drug allergy caused by topical administration
- Delayed corneal epithelial healing
- Corneal epithelial implantation cyst

9.2.3 Severity Classification of Adverse Events

The principal investigator and attending physician will determine the severity of all adverse events occurring during this clinical study by replacing them with the severity of adverse events based on the following classification of side effects of drugs, etc.

Grade 1: Adverse events considered mild.

Grade 2: Non-serious adverse events but not mild.

Grade 3: Adverse events considered serious. That is, depending on the patient's constitution or condition at the time of occurrence, it may lead to death or permanent functional impairment that hinders daily life.

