6.2 Observation Period: Visits 1~4 (Week 1~Week 8)

6.2.1 Visits 1 (Week 1), Visits 2 (Week 2), 3 (Week 4), 4 (Week 8)

Within each visit window, the following assessments and evaluations will be performed:

- 1) The investigator will inquire about the subject's symptoms and signs since the last visit and the occurrence of any adverse events, with detailed documentation in the electronic medical record.
- 2) Subjects will undergo ophthalmic examinations including: visual acuity (uncorrected and/or corrected), slit-lamp examination (anterior segment photography), intraocular pressure measurement, corneal OCT + panoramic OCT (weeks 1, 4, and 8), B-scan ultrasonography (week 2), confocal microscopy (weeks 4 and 8), corneal topography (weeks 1 and 4), biomechanical assessment (weeks 1 and 4), and fundus photography (week 4).

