9.1 Definition of Adverse Events

An adverse event is any unfavorable or unintended sign, symptom, or disease that occurs in a subject, regardless of whether it is related to the sutureless hydrogel repair of corneal stromal wounds or other treatments.

Furthermore, in this clinical study, planned hospitalizations and examinations before study initiation, as well as hospitalizations specified in the clinical study protocol, are not considered adverse events.

Among adverse events, those meeting the following conditions are called serious adverse events:

Resulting in death (Fetal)

Life-threatening

Requiring therapeutic hospitalization or prolonging hospitalization

Resulting in persistent/significant disability/incapacity

Congenital anomaly/birth defect

Other serious events equivalent to the above

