10.1 Safety Evaluation Items

The primary safety evaluation item: [All adverse events including systemic symptoms].

The secondary safety evaluation items: [Adverse events caused by hydrogel filling] and [Adverse events caused by surgical procedures], which mainly include elevated intraocular pressure, ocular surface inflammatory reaction, hydrogel displacement or detachment, corneal infection, delayed corneal epithelial healing, and decreased corneal endothelial morphology and density, with the judgment criteria

determined by the investigator.

Primary Outcome Measures and Judgment Criteria:

Delayed corneal epithelial healing

Judgment criteria: Corneal epithelium remains unhealed for 7 consecutive days as specified in 7.4.2. If delayed healing is observed during follow-up, timely adjustment of medication is required.

Infection

Judgment criteria:

- ① Severe conjunctival hyperemia accompanied by ciliary hyperemia and purulent discharge as per 7.4.1 (Conjunctival findings);
- ② Corneal infiltration and decreased corneal clarity in the hydrogel-filled area as per 7.4.2 (Corneal findings).

Infection is diagnosed when either ①+② or ② alone is present.

Hydrogel detachment

Judgment criteria:

- ① Depression in the hydrogel-filled area as observed under 7.4.2 (Corneal findings);
- ② Decreased thickness of the hydrogel-filled area detected by corneal OCT (7.3.3);
- ③ Decreased corneal thickness in the hydrogel-filled area detected by corneal topography (7.3.4).

Hydrogel detachment is diagnosed when ① and/or ② and/or ③ is present.

Furthermore, considering the occurrence of side effects and abnormal changes in clinical laboratory values during this clinical study, the overall safety of each subject will be graded into the following four categories:

- ① **Safe:** No side effects or abnormal changes in clinical laboratory values during the study period.
- ② **Basically safe:** Mild study-related side effects occurred during the study period (relieved/resolved without special treatment), or clinically insignificant abnormal changes in clinical laboratory values occurred (resolved upon re-examination without

intervention).

③ **Safety concerns:** Moderate study-related side effects occurred during the study period (relieved/resolved only after symptomatic treatment), or clinically significant abnormal changes in clinical laboratory values occurred (requiring intervention/re-examination monitoring).

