④ **Unsafe:** Severe study-related side effects occurred during the study period (requiring drug discontinuation/targeted treatment, or even endangering the subject's health), or marked abnormal changes in clinical laboratory values occurred (indicating organ dysfunction, requiring immediate intervention/drug discontinuation).

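### Section 9.2.3 grades severity by seriousness and is not tied to the levels in 10.1; separately, the Safe category can be met without any postoperative laboratory test

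*Protocol*

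**What the plan says.** Sections 2.1 and 3.3.1 make the severity of adverse events part of the primary safety evaluation. Section 9.2.3 supplies the scale:

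- "Grade 1: Adverse events considered mild"
- "Grade 2: Non-serious adverse events but not mild"
- "Grade 3: Adverse events considered serious", explained to mean that, depending on the patient, "it may lead to death or permanent functional impairment that hinders daily life"

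Section 9.1 defines serious adverse events by a longer list, which includes "Requiring therapeutic hospitalization or prolonging hospitalization". The items to be recorded for each event in 9.4 include severity but not seriousness.

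Section 10.1 then places each subject in one of four overall categories. Safe requires "No side effects or abnormal changes in clinical laboratory values during the study period". The other three use mild, moderate and severe study-related side effects, each described by the treatment needed, or laboratory changes of increasing importance. The worst category, Unsafe, begins "Severe study-related side effects occurred during the study period".

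Section 9.2 makes clinically significant laboratory changes from preoperative levels reportable as adverse events. Section 7.5.1 lists the blood and urine panel without saying when it is done. For Weeks 1 to 8, section 6.2.1 asks for symptoms and adverse events and then says "Subjects will undergo ophthalmic examinations including: visual acuity (uncorrected and/or corrected), slit-lamp examination", followed by further eye examinations.

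**The concern.** Severity (how intense an event is) and seriousness (whether it meets a regulatory outcome criterion) are different properties. A scale that moves from one to the other between Grades 2 and 3 cannot show how intense the non-serious events were. Most local eye reactions could well fall in that group. In a 30-subject single-arm study with safety as the primary objective, the severity table is a main result, so the loss matters.

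The laboratory clauses raise a different problem. A category defined by the absence of abnormal changes does not distinguish a subject who was tested and normal from one who was never tested. If the two are pooled, the count of Safe subjects looks more reassuring than the data allow.

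**Working it through.** The protocol gives no figure on this point to reproduce. Its sample size of 30 (11.1) is stated without an event rate or precision target. The check is mainly a comparison of sections.

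**Severity scale**

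1. Take a severe, non-serious event. It is not mild, so it is not Grade 1. It is not serious, so it is not Grade 3. It must be Grade 2.
2. Take a moderate, non-serious event. The same steps give Grade 2. The scale cannot separate the two.
3. Section 9.2.4 counts a fall of at least one grade as one form of improvement. If the 9.2.3 grades are meant, a non-serious event easing from severe to moderate shows no change of grade.
4. Take an event that only prolongs the hospital stay. By the 9.1 list it is serious, which points to Grade 3. By the explanation inside 9.2.3 it is not serious unless it may lead to death or permanent impairment, which points to Grade 2. The protocol does not say which meaning governs.
5. Take a related, non-serious event that needs targeted treatment. It is Grade 2 in 9.2.3, the middle grade, and can be Unsafe in 10.1, the worst category. No mapping resolves this.
6. Seriousness is not a listed item in 9.4, so the grade is the only listed item that carries it, and only partly.

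**Laboratory clauses**

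1. Planned postoperative contacts in Section 6: day 1 (6.1.5), discharge (6.1.6), and Weeks 1, 2, 4 and 8 (6.2.1), six in all. Contacts that list a blood or urine test: 0 of 6.
2. Time points for the panel in 7.5.1: none. The next section, 7.5.2, is headed as preoperative.
3. Unscheduled visits (6.3) are arranged when a subject has discomfort, signs or symptoms, so they would not routinely supply values for symptom-free subjects.
4. A subject with no side effects and no postoperative test has no recorded abnormal change, and so meets the literal wording of Safe.

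**Why the denominator matters (illustration only)**

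With 0 abnormalities among m tested subjects, the exact one-sided upper 95% bound on the true rate is 1 − 0.05^(1/m).

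| Tested, m | Upper bound |
|---|---|
| 30 | 9.5% |
| 15 | 18.1% |
| 5 | 45.1% |
| 0 | none |

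Suppose no subject has side effects, a fraction t is tested, the true abnormality rate is p, and untested subjects are counted as normal. The expected number classed as Safe is 30 × (1 − p × t). The protocol gives no p; assume 10%, with a range of 5% to 20%.

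- All tested (t = 1): 30 × 0.90 = 27, with a range of 28.5 to 24.
- None tested (t = 0): 30, whatever p is.

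**The case against.** Four counter-arguments deserve weight.

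First, a reader might infer that a severe non-serious event will be classed under safety concerns rather than Unsafe. The protocol does not support that. Section 10.1 never refers to Grades 1 to 3. It has its own treatment-based descriptions and does not require seriousness for Unsafe. The loss of information is therefore certain only in the 9.2.3 grade. At 10.1 the fault is two unlinked scales.

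Second, a reader might infer that a serious event through prolonged hospitalization has no grade at all. That follows only if the 9.1 meaning is used to rule out Grade 2 and the 9.2.3 meaning to rule out Grade 3. Under either meaning alone the event has a grade. What stands is that the grade depends on which meaning is used.

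Third, a reader might infer that none of the 30 subjects will have a postoperative laboratory value and that all 30 pass the laboratory part by default. Section 6 does not support that, because it names no preoperative blood or urine test either (6.1.3), although the exclusion criteria in 4.2 need fasting glucose and infection status. Section 6 is evidently not a full laboratory schedule. The comparison in 9.2 and the re-examination in 10.1 presuppose repeat testing. What stands is that no postoperative time point is stated anywhere.

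Fourth, counting an untested subject as Safe is not an explicit rule, and 11.5 sends missing data to case-by-case decisions. That is correct, but nothing in the protocol prevents such a classification, and a decision made case by case can be made after the results are known.

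**Conclusion.** The point holds in two separate parts.

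On severity, 9.2.3 puts every severe non-serious event in the same grade as moderate ones, uses a narrower meaning of serious than 9.1, and is not mapped to 10.1. This follows from the wording alone and needs no assumption. How many events are affected cannot be stated, because the protocol gives no expected rates. It would be too strong to say that the overall category in 10.1 is wrong for these events; the supportable statement is that the two scales can disagree.

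On laboratory safety, 9.2 and 10.1 depend on postoperative changes for which the protocol fixes no time, and the literal definition of Safe does not require a test. The consequence is limited to subjects who have no side effects and no postoperative value. It rests on reading a missing value as no abnormal change, which the text allows but does not order. The numerical illustration depends on an assumed abnormality rate and is not a forecast.

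The severity scale, the safety categories and the visit schedule are all fixed in the protocol, so this should be settled there before enrolment.

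**What to change.** **Severity.** Define Grades 1, 2 and 3 in 9.2.3 as mild, moderate and severe intensity, and use the same levels in 10.1. Record seriousness as a separate yes/no item, by the 9.1 list, among the case report form items in 9.4. The treatment-based descriptions in 10.1 should not simply be copied as intensity definitions. Section 8.4.2.2 prescribes targeted treatment for infection in general, so a scale based on treatment would put every infection at the top whatever its intensity.

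**Laboratory.** Reconcile 7.5.1 and Section 6 with the laboratory clauses in 9.2 and 10.1, so that the protocol states whether and when postoperative values are obtained. Report the laboratory part of the overall safety grade only for subjects with a postoperative value, with the number tested as the denominator. Class the others as not evaluated for laboratory safety. Deleting the laboratory clause from 10.1 alone would not solve the problem, because 9.2 already turns clinically significant laboratory changes into adverse events.

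**Cost.** Small wording changes in 9.2.3, 10.1, 7.5.1 and Section 6, and one added case report form item. Fewer subjects may be reported as fully Safe, and the study can claim laboratory safety only for those it tested.

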9.2.4 Adverse Events Outcome

The outcome of adverse events is classified as follows:

Recovery	Disappearance or resolution of symptoms/signs, normalization of test values, or recovery to pre-administration values.
Improvement	Reduction in the severity of symptoms/findings by at least 1 grade, near disappearance of mild symptoms/findings, or recovery of test values to near pre-administration values.

Unrecovered	No change in symptoms/findings or test values, worsening of the severity compared with the time of occurrence in the follow-up data on the last day of the observation period, irreversible congenital abnormalities, death in which the adverse event is not the direct cause and the adverse event remains unrecovered, recovery with sequelae, or partial recovery of symptoms/findings but partial confirmation as sequelae.
Death	A direct correlation is confirmed between death and the adverse event. Here, "confirmation of direct correlation" means that the adverse event is the cause of death or the adverse event significantly contributed to death. The outcome of an adverse event judged (presumed) to be an indirect cause of death in the same case is not considered "death".
Unknown	Cases where follow-up cannot be performed as described in the clinical study protocol after transplantation due to transfer, relocation, etc.

9.2.5 Outcome Date of Adverse Events

Record the date of recovery, improvement, unrecovery, or death during or after treatment. In addition, if the outcome date cannot be accurately specified, record the date of confirming the outcome content.

9.2.6 Correlation between adverse events and trial procedures and sutureless hydrogel repair of corneal wounds

The correlation with trial procedures and sutureless hydrogel repair of corneal wounds will be determined according to the following four categories.

Definitely related: Clear temporal correlation (including the course after surgery) and evidence of confirmed correlation;

Probably related: Clear temporal correlation (including the course after surgery), and factors other than the trial treatment, such as the primary disease, comorbidities, concomitant medications, and concurrent treatments, can be basically excluded;

Possibly related: Clear temporal correlation (including the course after surgery), other factors such as the primary disease, comorbidities, concomitant medications, and concurrent treatments can also be presumed, but the possibility caused by the trial treatment cannot be excluded;

Unrelated: No temporal correlation. It can be presumed to be caused by other factors such as the primary disease, comorbidities, concomitant medications, and concurrent treatments.

9.3 Management When Adverse Events Occur

During the subject's study participation, the principal investigator and attending physician will conduct necessary and appropriate examinations/observations and pay attention to the subject's safety. When an adverse event occurs, ensure that appropriate treatment is implemented,

pay attention to the subject's safety, and ensure that specialist diagnosis is obtained when necessary to strive to identify the cause.

In addition, during and after the subject's study participation, adequate medical measures will be taken for clinically significant serious adverse events related to the study.

After the end of the observation period, from the perspective of ensuring safety and scientific rationality, follow-up will be performed within the scope of insurance-based medical treatment if necessary. If it is known that a disease, disability, death, or infection suspected to be caused by the provision of this surgical trial has occurred, the principal investigator and attending physician shall promptly report the situation to the administrator of the medical institution performing regenerative medicine.

9.4 Adverse Events Recording

If a new adverse event occurs during the study period, record the following items in the adverse event column of the case report form.

Event name

Onset date

Severity

Outcome (recovery, improvement, unrecovered, death, unknown)

Outcome date

Correlation with trial procedures and transplantation of autologous

urine-derived epithelial cells

Management (discontinuation/continuance of the study, and treatment content for the adverse event)

9.5 Defects of Sutureless Ophthalmic Hydrogel for Corneal Defect Repair

Quality defects of the sutureless hydrogel refer to deviations in product quality that may occur after release determination and before delivery to the operating room or administration to the subject. Specifically, if any of the following defects are confirmed in the sutureless hydrogel, they will be recorded in the case report form:

- 1) Failure of the hydrogel to form a gel upon UV curing in vitro.
- 2) The hydrogel remains liquid at temperatures below 20°C.
- 3) The hydrogel fails to dissolve at 37°C.
- 4) White turbidity is observed in the hydrogel.
- 5) Damage to the packaging container is confirmed.
- 6) The product is not protected from light during transportation.
- 7) Other unexpected deviations.

The following items will be recorded in the case report form:

Implantation performed (1. No, 2. Yes)

Date of implantation

Date of defect occurrence

Defect classification (1. Contamination, 2. Defective product, 3. Performance, 4. Other)

Details of the defect

Presence of adverse events related to the defect (1. No, 2. Yes; if "Yes", record in the adverse events section)

9.6 Reporting of Adverse Events and Defects

When the following adverse events are known to occur during the implementation of this clinical study, the principal investigator and attending physician shall promptly report them to the administrator of the implementing medical institution.

10. Evaluation Items

10.1 Safety Evaluation Items

The primary safety evaluation item: [All adverse events including systemic symptoms].

The secondary safety evaluation items: [Adverse events caused by hydrogel filling] and [Adverse events caused by surgical procedures], which mainly include elevated intraocular pressure, ocular surface inflammatory reaction, hydrogel displacement or detachment, corneal infection, delayed corneal epithelial healing, and decreased corneal endothelial morphology and density, with the judgment criteria

determined by the investigator.

Primary Outcome Measures and Judgment Criteria:

Delayed corneal epithelial healing

Judgment criteria: Corneal epithelium remains unhealed for 7 consecutive days as specified in 7.4.2. If delayed healing is observed during follow-up, timely adjustment of medication is required.

Infection

Judgment criteria:

- ① Severe conjunctival hyperemia accompanied by ciliary hyperemia and purulent discharge as per 7.4.1 (Conjunctival findings);
- ② Corneal infiltration and decreased corneal clarity in the hydrogel-filled area as per 7.4.2 (Corneal findings).

Infection is diagnosed when either ①+② or ② alone is present.

Hydrogel detachment

Judgment criteria:

- ① Depression in the hydrogel-filled area as observed under 7.4.2 (Corneal findings);
- ② Decreased thickness of the hydrogel-filled area detected by corneal OCT (7.3.3);
- ③ Decreased corneal thickness in the hydrogel-filled area detected by corneal topography (7.3.4).

Hydrogel detachment is diagnosed when ① and/or ② and/or ③ is present.

Furthermore, considering the occurrence of side effects and abnormal changes in clinical laboratory values during this clinical study, the overall safety of each subject will be graded into the following four categories:

- ① **Safe:** No side effects or abnormal changes in clinical laboratory values during the study period.
- ② **Basically safe:** Mild study-related side effects occurred during the study period (relieved/resolved without special treatment), or clinically insignificant abnormal changes in clinical laboratory values occurred (resolved upon re-examination without

intervention).

③ **Safety concerns:** Moderate study-related side effects occurred during the study period (relieved/resolved only after symptomatic treatment), or clinically significant abnormal changes in clinical laboratory values occurred (requiring intervention/re-examination monitoring).

④ **Unsafe:** Severe study-related side effects occurred during the study period (requiring drug discontinuation/targeted treatment, or even endangering the subject's health), or marked abnormal changes in clinical laboratory values occurred (indicating organ dysfunction, requiring immediate intervention/drug discontinuation).

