8.4.2 Expected harms

8.4.2.1 Hydrogel detachment or displacement

Judgment criteria: Hydrogel displacement or absence in the graft area observed on slit-lamp examination.

Management method: The principal investigator and physicians performing regenerative medicine will discuss the treatment plan during the observation period.

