10.2 Efficacy Evaluation Items

Corneal Thickness

Judgment method: At each visit, based on the corneal thickness examination results described in 7.3.3, a corneal thickness improvement effect is considered present when the thickness reduction in the filled defect area does not exceed 20%.

Evaluation method:

① Effective: The improvement effect is observed at least once before Visit 4 and in a total of two or more visits including the final assessment.

② Ineffective: All cases other than ①.

Corneal Clarity (Degree of Corneal Opacity)

Judgment method: At each visit, based on the slit-lamp examination findings of the cornea described in 7.4.2, corneal clarity is considered good (stromal transparency after repair) when the corneal opacity score is ≤ 2 .

Evaluation method:

- ① Effective: Good corneal clarity is observed at least once before Visit 4 and in a total of two or more visits including the final assessment.
- ② Suggestive effective: Corneal thickness improvement effect is observed at least once before Visit 4, but corneal clarity is judged as poor at the final assessment.
- ③ Ineffective: All cases other than ① and ②.

Visual Acuity and/or Corrected Visual Acuity

Judgment method: At each visit, based on the visual acuity examination results described in 7.3.1, using distance decimal visual acuity, a visual acuity improvement effect is considered present when the visual acuity improves by at least one grade compared with the baseline (preoperative) assessment.

Evaluation method:

- ① Effective: The improvement effect is observed at least once before Visit 4 and in a total of two or more visits including the final assessment.
- ② Ineffective: All cases other than ①.

Judgment when "Insufficient Therapeutic Effect"

Judgment method: When at the final assessment, hydrogel degradation exceeds 20%, corneal opacity score is ≥ 3 , and visual acuity is lower than baseline (preoperative visual acuity), the outcome is defined as "insufficient therapeutic effect."

11. Statistical Matters

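### Section 10.1 diagnoses hydrogel detachment from any unquantified thinning, while 10.2 counts thinning of up to 20% as an improvement effect and 8.4.2.1 uses a different, slit-lamp criterion

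*Protocol*

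**What the plan says.** **Detachment in Protocol 10.1.** Three signs are listed. The first is a depression of the filled area on corneal examination. The second is "Decreased thickness of the hydrogel-filled area detected by corneal OCT (7.3.3". The third is "Decreased corneal thickness in the hydrogel-filled area detected by corneal topography (7.3.4". The combination rule is "Hydrogel detachment is diagnosed when ① and/or ② and/or ③ is present". No size of decrease, reference examination or confirmation is given.

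**Thickness in Protocol 10.2.** On the OCT examination of 7.3.3, "a corneal thickness improvement effect is considered present when the thickness reduction in the filled defect area does not exceed 20" per cent. This is a judgment at each visit. A patient is rated effective only if the effect is seen at least once before Visit 4 and at two or more visits including the final assessment. The reference for the reduction is not stated here either. The same section uses degradation above 20% as one part of insufficient therapeutic effect.

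**Detachment in Protocol 8.4.2.1.** The criterion is "Hydrogel displacement or absence in the graft area observed on slit-lamp examination". A discussion of the treatment plan is attached to it.

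**Status of the item.** In 10.1 the detachment rule stands under the heading "Primary Outcome Measures and Judgment Criteria". Earlier in the same section we read "The secondary safety evaluation items: [Adverse events caused by hydrogel filling] and [Adverse events caused by surgical procedures], which mainly include elevated intraocular pressure"; that list goes on to name displacement or detachment and leaves the criteria to the investigator. Section 3.3.1 lists it among the primary evaluation items.

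**Examinations.** Slit-lamp examination is done at every visit. Section 6.2.1 schedules "corneal OCT + panoramic OCT (weeks 1, 4, and 8"), and topography at Weeks 1 and 4. Both are also done at discharge (6.1.6).

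**The concern.** Safety is the primary objective (2.1), and whether the gel stays in place is one of the main things a first clinical study of this material should show. The protocol gives three rules for reading the same eye, and no section says which governs.

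Two consequences follow. First, the safety and efficacy tables can describe one thickness reading in opposite terms. Second, the count of detachments depends on which section the assessor has in mind. Under 10.1 it can include gel that is in place but slightly thinner, or not thinner at all but measured a little lower. The study is open-label with a single arm, so no comparator shows how many flagged eyes are artefact. Section 10.1 also names detachment among the adverse events caused by hydrogel filling, so such flags could pass into the adverse event tables. It is likewise unclear whether an eye flagged only under 10.1 falls under the management step in 8.4.2.1.

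**Working it through.** **1. The rules side by side.** Take an eye whose filled area measures 10% thinner on OCT at one visit, with no depression and with the gel in place at the slit lamp.

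| Section | Criterion applied | Result |
|---|---|---|
| 10.1 | any decrease on OCT; one sign suffices | detachment |
| 10.2 | reduction of 20% or less | improvement effect at that visit |
| 8.4.2.1 | displacement or absence at the slit lamp | no event |

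The first two results coincide for every OCT reduction above 0% and up to 20%. This needs no assumption beyond a common reference for the two sections. The topography sign has a further difficulty: 7.3.4 describes topography as measuring curvature and morphology and does not mention thickness.

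**2. No figure to reproduce.** The protocol gives no expected detachment rate, no measurement error and no numerical basis for the 30 cases. What follows only illustrates how far the count depends on the unstated reading rule.

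**3. Any numerical drop counts.** Assumptions, none of them in the protocol: the discharge examination is the reference, true thickness is stable, and errors are continuous and exchangeable between visits. The chance that at least one of k later readings lies below the reference is k/(k+1).

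- OCT, k = 3 (Weeks 1, 4, 8): 3/4 = 75%, or 0.75 × 30 = 22.5 eyes.
- Topography, k = 2 (Weeks 1, 4): 2/3 = 67%, or 20 eyes.
- Either, if the two instruments' errors are independent: 1 − (1/4 × 1/3) = 11/12 = 92%, or 27.5 eyes.

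If the two instruments agreed completely, the combined figure would fall back to the 75% for OCT alone. A simulation of 400,000 draws gave 0.750, 0.668 and 0.917.

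**4. Only drops beyond measurement error count.** Keep the same model with normal errors, but call a decrease only when it exceeds c = 1.96 × √2 = 2.77 measurement SDs. The probability is 1 − ∫ φ(x)[1 − Φ(x − c)]^k dx.

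- OCT: 6.3%, or 1.9 of 30 eyes.
- Topography: 4.5%.
- Either, if independent: 1 − (0.937 × 0.955) = 10.5%, or about 3 of 30 eyes.

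**5. With true thinning.** Assume linear thinning to a Week 8 mean of 0 to 15%, a between-patient SD of 5 points, an error SD of 1 to 5 points, the discharge reference, and any drop counted. The OCT sign then flags 70% to 99.9% of eyes. Between 69% and 96% are both flagged and rated effective on thickness over the OCT visits.

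**6. Schedule.** The slit-lamp sign is available at every visit. The OCT sign is not available at Week 2, and the topography sign is not available at Weeks 2 and 8. Detachment by visit is therefore ascertained with different tests.

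**The case against.** Several points on the other side are fair.

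- **The size of the noise problem is not established.** A reader might infer from the 92% that about 27 of 30 intact eyes will be recorded as detached. The documents do not support that as a forecast. It needs the discharge scan as reference, independent instrument errors, and a clinician who calls any numerical drop a decrease. If decreases are called only beyond measurement error, the result is about 6% to 11%. With the preoperative eye as reference, the noise model does not apply at all.
- **Thinning of 20% or less is not in itself an efficacy success.** It is a per-visit effect. An eye 10% thinner at Week 1 and 30% thinner at Week 8 is ineffective under 10.2.
- **Calling the rate uninterpretable goes too far.** The study is exploratory and descriptive, and no test or stopping rule uses the rate. Section 11.3 provides for measured values and changes from baseline, and 6.1.6 records hydrogel adherence, so thickness and slit-lamp findings could still be reported separately.
- **The schedule effect is minor**, since the slit lamp is used at every visit.
- **A reader might conclude that the slit-lamp criterion should govern.** The documents do not settle this. Section 7.3.3 assigns OCT to evaluate adhesion and filling, 10.1 has its own slit-lamp sign (depression), and 8.4.2.1 ties its criterion to management.

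None of this removes the conflict. A statistical analysis plan could set a reading rule, but the protocol already states incompatible diagnostic rules, and these have to be changed where they stand.

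**Conclusion.** The point holds as a conflict of definitions. Any OCT thinning above 0% and up to 20% meets the detachment rule in 10.1 and the improvement rule in 10.2 at the same visit, and need not meet 8.4.2.1. This follows from the wording if both sections use the same reference, which neither states. Applied literally, 10.1 yields a rate that mixes displacement, ordinary thinning and measurement error.

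How much it would be inflated cannot be fixed from the protocol. In a stable eye with the discharge reference, false flags range from about 6% (OCT only, drops beyond measurement error) to 92% (OCT or topography, any drop, independent errors). The width of that range is itself the result of leaving the threshold and reference open.

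The standing of the item is also unsettled. It cannot simply be called a primary outcome, because 10.1 also places it among the secondary safety items with criteria left to the investigator.

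**What to change.** 1. Reconcile 8.4.2.1, 10.1 and 10.2 into a single definition of detachment or displacement. Which signs make the diagnosis is for the investigators to decide.
2. State the reference examination in that definition and in the thickness rule of 10.2. If thickness remains a criterion for detachment, state the size of decrease that counts, so that the same thinning cannot be both a detachment and an improvement effect. If topography is kept as a source of thickness, make 7.3.4 agree.
3. Report hydrogel thickness loss as its own item: percentage change from the stated reference, and above 20% yes or no (the cut-off already in 10.2), at the visits where OCT is done.
4. State once whether detachment is a primary or a secondary safety item, and align 3.3.1 and both parts of 10.1. Remove either the reference to investigator-determined criteria or the fixed criteria for this item.

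The cost is wording in these sections and matching case report form fields. No new examinations are needed.
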